### Statistical Analysis

[figure not shown]
#### *For aim 1:*

[figure not shown]
The primary outcome is PLP indexed by VAS. PLP will be analyzed using intensity of pain over time. To analyze these data, we will initially build a mixed ANOVA model in which the dependent variable will be the outcome of PLP (such as VAS) and the independent variables will be group (active tDCS-MT; sham tDCS-MT; active tDCS and covered MT; sham tDCS- covered MT), time (baseline and after treatment and follow-up) and the interaction group\*time. In addition we will add the random variable ID to account for within subject’s variability and the repeated measures on time. We will initially perform this full model and, subsequently, post-hoc comparisons with corrections for multiple comparisons will be carried out initially to test our main hypotheses. Furthermore we will test the correlation in improvement between outcomes using Pearson’s correlation tests. P-values for secondary and exploratory outcomes will be determined without corrections for multiple comparisons. Finally we will apply a path analysis [60, 61] to the primary outcome data to determine if pain reduction associated with the combined intervention (tDCS and MT) is due to direct effects versus indirect effects through improvement in secondary outcomes. We propose that a direct effect of tDCS and MT on pain can be assumed if the treatment effect cannot be explained by changes in psychological or functional outcomes. Statistical models for pain will be developed using covariates that include site center, baseline

[figure not shown]
pain, psychological changes, functional changes, and the covariate treatment (main effect of treatment). To complete the path analysis separate regression models will be run to model the effects' of treatment on each outcome alone including all the secondary outcomes. Analyses of the secondary outcomes will be conducted in an exploratory manner (no correction for multiple comparisons). For the intention-to-treat analysis, we will use a conservative method and assume that participants will not improve from the last measured point. But we will also perform a sensitive analysis for the missing data using other methods such as completers only.

*For aim 2:*

The secondary outcomes are other pain measurements, psychological, neuropsychological and quality of life measurements and neurophysiological markers (as indexed by TMS and fMRI). Functional neuroimaging data will be analyzed using both Freesurfer image analysis suite combined with the FS-FAST functional data analysis package (Massachusetts General Hospital, Charlestown, MA) (<http://surfer.nmr.mgh.harvard.edu/>) and with Brain Voyager QX 1.9 software package (Brain Innovation, Maastricht, Netherlands). Briefly, a high resolution anatomical T1-weighted anatomical volume is used to reconstruct a cortical surface mesh and then inflated to allow viewing of sulcal activation. The functional preprocessing includes 3-D motion correction using the first volume alignment, high pass filtering to remove temporal linear trends, correction for slice time acquisition and spatial smoothing (Gaussian kernel, 5.0 mm FWHM). Subjects are screened for excessive motion (defined as a maximum tolerance of 3mm in any direction). Following co-registration of the preprocessed functional image with the high-resolution anatomical, data is transformed into standard Talairach space. Voxel time courses for each subject are fit by a general linear model (GLM) for statistical analysis. Each experimental condition is modeled by a boxcar regressor matching the condition time course. These boxcar regressors are then smoothed by a canonical hemodynamic response function [62]. Individual subject maps for each contrast of interest is generated by projecting the volume of significance values resulting from the GLM onto the reconstructed cortical surface mesh for each hemisphere in each subject. Statistical significance is set at a standard threshold criterion of  $p < 0.05$  corrected for multiple comparisons using a cluster-size threshold adjustment [63].

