## II. SPECIFIC AIMS

The specific aims of this experiment are as follows:

[figure not shown]
- **Aim 1: To evaluate the efficacy of tDCS and mirror therapy (MT) as rehabilitative tools for the management of chronic PLP patients.**

We will explore the aim 1 in a randomized factorial controlled trial in which patients will be assigned to one of four groups: active tDCS and active MT; sham tDCS and active MT; active tDCS and sham MT (which consists of using a covered mirror for the therapy); and both sham tDCS and sham MT (covered mirror).

The primary end point will be severity of pain measured by changes in PLP as indexed by a Visual Analog Scale (VAS). The study will require a total of 13 weeks to be completed. The first week, each patient will give daily reports of their pain using a VAS, accounting for their PLP experience in the past 24hs. This initial baseline week will be followed by 4 weeks of treatment (tDCS and/or MT) and a final 8-week follow-up period without any treatment to examine long-lasting effects of each therapy. *Our hypothesis is that the combined intervention (tDCS and MT) will result in a greater pain reduction as compared with any therapy alone and no therapy.*

- **Aim 2: To examine the mechanisms underlying PLP using two neurophysiological techniques.**

For each of the four groups described in aim 1, we will determine the neural correlates of the effect. We will use single-pulse and paired-pulse transcranial magnetic stimulation (TMS) to assess cortical mapping and cortical excitability changes associated with cortical reorganization. We will also use functional magnetic resonance imaging (fMRI) to assess brain changes, including the quantification of maladaptive cortical reorganization. Using fMRI, we will determine the changes in Blood-Oxygen-Level dependent activation between the sensory-motor cortex of the affected and unaffected side after the treatment. We will compare these neurophysiological parameters before and after treatment in each of the four groups. *Our hypothesis is that the combined group (tDCS and mirror therapy) will have a greater activation than any therapy alone and also than the no therapy group (sham tDCS and covered mirror). This effect will also be correlated with pain reduction.*

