**Visit 2**

Baseline Visit – (Approximate Time: 2 hours)

*This visit might be completed on the same day as the screening visit if time allows and the subject agrees.*

Baseline assessments:

- Visual Analogue Scale (VAS) for Pain
- Visual Analogue Scale (VAS) for Stump pain
- Visual Analog Scale (VAS) for Phantom Limb Sensation
- Visual Analog Scale (VAS) for Phantom Limb Telescoping
- Adapted Groningen Questionnaire After Arm Amputation
- Pain and Medication use diary\*
- Beck Anxiety Inventory
- Mini Mental State examination (MMSE)
- Stroop Test
- Health Survey SF-36
- Single and paired pulse TMS
- Side Effects Questionnaire for TMS

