**Visit 3**

fMRI Evaluation – (Approximate Time: 1 hour)

*\*\*Visits 1-3 may be completed on the same day or broken up into two or three separate visits as the subject prefers*

**Visit 4 – 12** (Approx Time: 45 minutes)

Intervention visits: tDCS + Mirror Therapy

*This visit will be scheduled within 1 week after the baseline measurements are done.*

In the first 2 weeks subjects will receive tDCS (\*sham or active) and mirror therapy (sham or active). There will be 10 stimulation visits to be completed in these 2 weeks (ideally Monday to Friday, 5 days each week). The subject will receive 20 minutes either of active or sham tDCS per day and 15 min of active or sham mirror therapy sessions. The subjects will receive the intervention according to the prior randomized group.

Before stimulation, the subject will complete the following assessments:

- VAS Phantom Limb Pain
- VAS for Stump pain
- VAS for Phantom Limb Sensation
- VAS for Phantom Limb Telescoping

After each session, subjects will complete the following assessments:

- Side Effects Questionnaire for tDCS
- VAS Phantom Limb Pain
- VAS for Stump pain
- VAS for Phantom Limb Sensation
- VAS for Phantom Limb Telescoping

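### The primary mixed ANOVA treats baseline VAS as a level of time and omits baseline pain and centre as covariates, although randomisation is stratified on both; adjusting for them costs little, for a gain of unknown size

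*Combined protocol and SAP*

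**What the plan says.** **Primary model.** For aim 1, the Statistical Analysis section sets out a mixed ANOVA of the VAS on group (four arms), "time (baseline and after treatment and follow-up") and group by time. It continues: "In addition we will add the random variable ID", to account for within-subject variability and the repeated measures on time. No covariate or residual covariance structure is listed. The tests of the main hypotheses are described only as "post-hoc comparisons with corrections for multiple comparisons will be carried out initially to test our main hypotheses", and no contrast is named. Specific Aims, Aim 1 describes the primary end point as "severity of pain measured by changes in PLP as indexed by a Visual Analog Scale".

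**Where the covariates appear.** Later in the same paragraph, after the path analysis is introduced: "Statistical models for pain will be developed using covariates that include site center, baseline" pain, then psychological changes, functional changes and treatment.

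**Randomisation.** The Randomization text under Screening Procedures stratifies by baseline pain (average VAS up to 6, or above 6) and by study centre.

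**Candidate baseline values.**
- Specific Aims: in the first week "each patient will give daily reports of their pain using a VAS", covering the past 24 hours.
- Visit 2: one "Visual Analogue Scale (VAS) for Pain".
- Visits 4 to 12: a VAS before each session. Of the start of treatment the plan says "This visit will be scheduled within 1 week after the baseline measurements are done", so seven daily reports are not assured.
- Pain and medication diary: the intensity of the strongest episode.

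**The concern.** If the tested contrast is group by time, as the wording about changes in pain suggests, the treatment effect is a difference in change scores. That gives up precision the trial could have from data it already collects. It also leaves the two stratification factors out of the efficacy model. When randomisation balances arms on pain and the test ignores this, the usual standard error is too large for a change-score test and the test becomes conservative.

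Two specification gaps add to this. The baseline value is not identified, and the possible gain depends heavily on which one is used. No covariance is stated beyond the random subject term. If that term is the only one, the model assumes equal variances and equal correlations between all visits, and the error rate of a baseline-to-post contrast then depends on whether those assumptions hold.

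**Working it through.** **The plan's own figure.** Sample size calculation gives means of 5.2 (SD 1.5) and 6.4 (SD 1.6), two-sided 0.05 and 80% power. Difference 1.2; pooled SD = sqrt((1.5² + 1.6²)/2) = 1.551. n per arm = 2 × (1.551 × (1.960 + 0.842)/1.2)² = 26.2, rounded up to 27; × 4 = 108. For attrition, 27 × 1.2 = 32.4, rounded up to 33; × 4 = 132. Both stated totals reproduce. The calculation compares scores in two groups and does not involve the baseline.

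**Assumptions below.** Difference 1.2, post-treatment SD 1.551, 27 per arm, uncorrected two-sided 0.05. The documents give no correlation or SD ratio.

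**Step 1: change score against baseline adjustment, ignoring stratification.** Set the post-treatment variance to 1. Let r be the single-day baseline-to-post correlation, c the correlation between days of the baseline week and m the number of days averaged.
- Baseline variance: k² = c + (1 − c)/m.
- Variance of change: 1 + k² − 2r.
- Variance after adjustment: 1 − r²/k².
- Their difference is (k − r/k)², which is never negative.

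Power (noncentral t, 52 df):

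| Baseline | r | c | Change variance | Adjusted variance | Change power | Adjusted power |
|---|---|---|---|---|---|---|
| Single day | 0.3 | – | 1.40 | 0.91 | 65.5% | 83.3% |
| Single day | 0.5 | – | 1.00 | 0.75 | 79.7% | 89.6% |
| Single day | 0.7 | – | 0.60 | 0.51 | 95.0% | 97.4% |
| 3-day mean | 0.3 | 0.3 | 0.933 | 0.831 | 82.3% | 86.4% |
| 7-day mean | 0.3 | 0.5 | 0.971 | 0.843 | 80.8% | 86.0% |
| 7-day mean | 0.3 | 0.3 | 0.800 | 0.775 | 87.7% | 88.7% |

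The gap runs from 17.8 points (83.3 − 65.5) to 1.0 (88.7 − 87.7). With a 7-day mean and c = r, it is 0.3 at r = 0.5 (95.8% against 96.1%).

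**Step 2: the random-subject-only test, ignoring stratification.** This test takes the variance of a change to be 2 × (mean variance − mean covariance over all visits). With baseline and three post-treatment visits, error df = (108 − 4) × 3 = 312 and the critical value is 1.968.
- Baseline-to-post 0.5, post-to-post 0.7: mean covariance 0.6, assumed 0.80, true 1.00. Effective cut-off 1.968 × sqrt(0.80/1.00) = 1.760; error about 7.8% (simulated 7.7%).
- 0.3 and 0.7: assumed 1.00, true 1.40; error about 9.6% (simulated 9.7%).
- All 0.5: assumed and true both 1.00; simulated 5.0%.
- 7-day mean baseline, all single-day correlations 0.3: mean variance (0.4 + 3)/4 = 0.85, assumed 2 × (0.85 − 0.3) = 1.10, true 0.80; about 2.1% (simulated 2.2%). Simulated power was 81.7%, against 89.4% for the change score and 90.0% adjusted.

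**Step 3: with the planned stratification.** Simulated with a single-day baseline, blocks of 4 and 8 within pain and centre strata, and a pain cut near the median. The stratifying value was either the analysed baseline or a value correlated 0.7 with it.

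| Correlations (baseline-to-post / post-to-post) | Random-subject-only type I error | Adjusted test's power advantage |
|---|---|---|
| 0.5 / 0.7 | 5.4% to 6.9% | about 2 to 5 points |
| 0.3 / 0.7 | 6.3% to 7.9% | about 2 to 5 points |
| all 0.5 | conservative, about 3% to 4% | about 7 to 8 points |

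The separate change-score test was also conservative (about 3% to 4%) and trailed the adjusted test by about 7 to 17 points. The adjusted test held 4.6% to 5.6% and had the highest power in every scenario. The 2-to-8-point range covers these three patterns only. If all correlations were 0.3, the random-subject test would assume 2 × (1 − 0.3) = 1.40, the true value. It would then behave like the change-score test, with a gap nearer to that test's.

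**The case against.** The strongest reply is that the planned analysis is valid. A change contrast is unbiased under randomisation, the gain cannot be sized from the documents, and with a well-averaged baseline it may be nil. The plan does name baseline pain and site centre as covariates in models for pain, so adjustment may have been intended. The covariance text mentions repeated measures on time and can be read as a random subject plus a repeated effect. The contrast is not named, and the figures use an uncorrected 0.05 although the plan corrects its post-hoc tests.

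Most of this stands and limits the point. It does not remove it. The covariate sentence follows the introduction of the path analysis and lists post-randomisation changes, so it does not supply an efficacy model. If adjustment was intended, one sentence would say so.

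Three stronger readings are tempting and are not supported:
- *The type I error is 8% to 10%.* The 7.7% to 9.7% figures hold only without the pain and centre stratification that this trial uses. They also rest on one reading of the covariance text and on assumed unequal correlations.
- *Up to 18 power points are lost.* That figure compares a separate two-group change-score test on a single-day baseline at r = 0.3 with adjustment. The plan describes a pooled four-group model.
- *The sample size is wrong.* The 27, 108 and 132 reproduce and do not depend on this choice.

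**Conclusion.** The point holds as a matter of efficiency and specification, and is worth considering. The primary model leaves both stratification factors out of its covariates and carries baseline as a response level. Its group-by-time contrast cannot be more precise than a baseline-adjusted one, apart from about one degree of freedom.

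The size is unknown. The simulated gains assume a single-day baseline and baseline-to-post correlations of 0.3 to 0.5, and they shrink to a point or nothing against the change score if a well-averaged seven-day baseline is used. If the random subject term is the only covariance term, and post-treatment visits correlate more with each other than with baseline, the baseline-to-post contrast may run at about 5.5% to 8% under stratification. With equal correlations it is conservative instead. No bias has been shown in the planned contrast.

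**What to change.** - Make post-baseline VAS the outcome. Include continuous baseline VAS, baseline by time, centre, group, time and group by time, with an unstructured within-subject covariance. A constrained longitudinal model with a common baseline mean is an alternative; it should also carry centre.
- State that the adjustment covers both stratification factors, baseline pain and centre.
- Name one baseline VAS, on the same scale and recall period as the post-treatment VAS. The strongest-episode diary score does not meet this. If the mean of the daily reports is chosen, say how fewer than seven reports are handled.
- Name the primary contrast and its time point.
- State that the path models containing post-randomisation changes are separate from the efficacy analysis.

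The cost is SAP wording and a few degrees of freedom. Baseline VAS and centre are already recorded, and the sample size need not change on this account.

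### No visit is named as deciding the Aim 1 comparison, and the promised multiplicity correction has no stated family across contrasts and visits

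*Combined protocol and SAP*

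**What the plan says.** Section II (Specific Aims, Aim 1) makes change in PLP on a VAS the primary endpoint, with no time point. Its hypothesis is that "the combined intervention (tDCS and MT) will result in a greater pain reduction as compared with any therapy alone and no therapy", again with no time point. The same section describes four weeks of treatment and then "a final 8-week follow-up period without any treatment to examine long-lasting effects of each therapy".

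Section VI (Statistical Analysis, For aim 1) states that "PLP will be analyzed using intensity of pain over time". It sets up a mixed ANOVA with a random subject term. The independent variables are the four-level group, "time (baseline and after treatment and follow-up) and the interaction group\*time". After the full model, "post-hoc comparisons with corrections for multiple comparisons will be carried out initially to test our main hypotheses". It does not name the correction method, the contrasts, or the visits at which they are taken. Secondary and exploratory outcomes are explicitly left uncorrected.

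The visit descriptions in section V put PLP VAS at Visit 13 (last tDCS session), Visit 14 (last home mirror therapy session), Visit 16 (about 4 weeks later) and Visit 17 (about 8 weeks later), as well as around each stimulation session. The sample size section attaches no time point to the means it borrows.

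**The concern.** Relief at the end of treatment and relief that lasts eight weeks are different conclusions. They can disagree when an effect fades or appears late. With no deciding visit, the Aim 1 answer can be read at several times, and the correction can be applied in two ways:

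- **Within each visit only.** Error across visits is then not controlled, and a result at whichever visit looks best could be reported as the Aim 1 finding.
- **Across contrasts and visits together.** Error is controlled, but power goes to follow-up comparisons that the sample size did not allow for, and a real end-of-treatment effect may be missed.

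This gap does not depend on how long each therapy has been stopped at each visit. The decision would be just as undefined if both therapies ended on the same day.

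**Working it through.** **1. The plan's own figure.** Inputs (Sample size calculation): means 5.2 (SD 1.5) and 6.4 (SD 1.6), two-sided alpha 0.05, power 80%.

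- Pooled SD = sqrt((1.5² + 1.6²)/2) = 1.551; d = 1.2/1.551 = 0.774.
- n per arm = 2 × (1.960 + 0.842)²/0.774² = 26.2, rounded up to 27; 4 × 27 = 108, as stated.
- Attrition: 27 × 1.2 = 32.4, rounded up to 33; 4 × 33 = 132, as stated.

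The stated size therefore matches one two-arm comparison, at one time, at undivided alpha 0.05.

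**2. Size of the possible family.** The hypothesis gives three contrasts: combined versus mirror therapy alone, versus tDCS alone, and versus neither. Read literally, the time factor has two post-baseline levels. Visits 14, 16 and 17 make three, and adding Visit 13 makes four. The family is then 3 × 2 = 6, 3 × 3 = 9 or 3 × 4 = 12 tests.

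**3. Error if only the three contrasts within each visit are corrected.** This was simulated with 400,000 runs of four equal arms under the global null. For contrast j at visit k, z = (combined mean − mean of arm j)/SE. At least one |z| above the cut-off counts as a false positive. Cut-offs are 2.39 (Bonferroni, 0.05/3) and 2.35 (Dunnett). The documents give no between-visit correlation, so it is assumed and varied.

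| Visits | Bonferroni, corr. 0.5 | Dunnett, corr. 0.5 | Bonferroni, corr. 0.9 | Dunnett, corr. 0.9 |
|---|---|---|---|---|
| 1 | 4.5% | 5.0% | 4.5% | 5.0% |
| 2 | 8.2% | 9.2% | 6.3% | 7.1% |
| 3 | 11.5% | 12.8% | 7.7% | 8.6% |
| 4 | 14.4% | 16.0% | 8.7% | 9.7% |

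At correlation 0.3 the range is 12.2-13.6% for three visits and 15.9-17.6% for four.

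**4. How the figure depends on the rule** (correlation 0.5):

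- *Only results favouring the combined arm count:* 6.4% (three visits) and 8.1% (four) with Dunnett, against a nominal 2.5%.
- *All three contrasts must win at the same visit, corrected cut-off kept:* about 0.1% under the global null. In the worst case (one contrast null, the other two certain) it is 2.2-2.5% for three visits and 2.8-3.2% for four.
- *Post-hocs run only after a significant group-by-time test* (27 per arm, change from baseline, Bonferroni by 3): about 3% under the global null with three or four visits.
- *Same gate, but all three active arms beat double sham by d = 0.774 and the combination adds nothing:* the gate passes in at least 84% of runs. A false difference between the combination and a single therapy at some visit occurs in about 8% of runs (three visits) or 10% (four), counting both directions. At one visit these two contrasts could give at most 2 × 0.0167 = 3.3%.

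**5. Power if the correction spans visits.** Noncentral t, d = 0.774, 27 per arm, assuming the same d for each contrast:

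| Family | Alpha per test | Power per contrast |
|---|---|---|
| One contrast, one visit | 0.05 | 79.7% |
| 3 contrasts, one visit | 0.0167 | 64% |
| 3 contrasts × 3 visits | 0.0056 | 49% |
| 3 contrasts × 4 visits | 0.0042 | 45% |

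The fall from 80% to 64% comes from having three contrasts. Only the fall from 64% to 49% or 45% comes from the visits. Bonferroni is conservative here because the contrasts share an arm and the visits are correlated.

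**The case against.** The strongest reply is that the plan is more protected than the 11-16% suggests. The full model comes first. If its group-by-time test is a gate, error under the global null is about 3%. The hypothesis also reads naturally as the combination beating all three comparators, and on that rule inflation almost disappears. The two-sided figures count visits where the combined arm does worse, which nobody would report as success. Finally, the Specific Aims place the end of treatment at four weeks and give follow-up its own purpose, so the end of treatment looks like the implied main reading.

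Much of this stands, and it limits the size of the problem. It does not close the gap. Section VI gives an order (model, then post-hocs) but does not make the second conditional on the first. Such a gate would not protect the combined-versus-single contrasts when the single therapies work, and those contrasts are central to Aim 1. The all-three rule is not stated. Follow-up sits in the same primary model, unranked, and even the post-treatment level could mean Visit 13 or Visit 14.

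A reader might also infer that the trial will run at a 13-16% false-positive rate, or that 108 is miscalculated. The documents support neither. That rate needs an any-contrast, any-visit, ungated, two-sided rule that the plan does not adopt, and 108 reproduces for the single comparison it describes.

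**Conclusion.** The point holds as a specification gap of moderate weight that should be corrected. No visit decides Aim 1, and the family for the correction is undefined.

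The error cost is a range, not one number. On the least protected reading at correlation 0.5 it is about 8-9% (two visits), 11-13% (three) or 14-16% (four). At correlation 0.9 it is about 8-10% for three or four visits. Counting only favourable results halves these figures. An all-three rule nearly removes the inflation, and gating brings error to about 3% under the global null only. If the correction spans visits instead, the cost is power per contrast of 49% or 45% rather than 64%.

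These results rest on an assumed exchangeable correlation between visits, on Bonferroni or Dunnett standing in for the unnamed correction, and on the plan's d = 0.774 applying to every contrast.

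**What to change.** In section VI, For aim 1, state that:

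1. The primary comparison is the change in PLP VAS from baseline to Visit 14, the end of the four-week treatment period in the Specific Aims, estimated from the same mixed model.
2. The three combined-arm contrasts at that visit are corrected by a named method, for example Dunnett or Holm.
3. Aim 1 success requires either all three contrasts or any one of them, whichever the sponsor intends.
4. Visits 13, 16 and 17 are secondary and reported with confidence intervals. Alternatively, Visit 16 and then Visit 17 are tested in fixed order, only after success at Visit 14 as defined in item 3.

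This needs wording only: no new data or visits. The downside is that a benefit seen only at follow-up could not be the primary result.

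The change does not restore 80% power. Three Bonferroni-corrected contrasts at 27 per arm have about 64% each, so the power statement should be redone for the chosen rule. As a guide, 80% per contrast at alpha 0.0167 needs about 35 per arm by the plan's normal approximation: 4 × 35 = 140 evaluable, or 140/0.8 = 175 enrolled at 20% attrition.

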**Visit 13**

Last day of tDCS session + Mirror Therapy – (Approx Time: 2 hours)

Before stimulation, the subject will complete the following assessments:

- VAS Phantom Limb Pain
- VAS for Stump pain
- VAS for Phantom Limb Sensation
- VAS for Phantom Limb Telescoping

After each session, subjects will complete the following assessments:

- Visual Analogue Scale (VAS) for phantom limb pain
- Visual Analogue Scale (VAS) for Stump pain
- Visual Analog Scale (VAS) for Phantom Limb Sensation
- Visual Analog Scale (VAS) for Phantom Limb Telescoping
- Pain and medication use diary
- Stroop Test
- Beck Anxiety Inventory

- Beck Depression Inventory
- Side Effects Questionnaire for tDCS
- Blinding Questionnaire
- Single and paired pulse TMS
- Side Effects Questionnaire for TMS

**After the first 2 Weeks combined intervention (sham/active tDCS plus sham/real mirror therapy) at the Neuromodulation Center in front of the therapist, subjects will continue mirror therapy for 10 additional sessions over the course of ~ 2 weeks at home.**

2 weeks of home Mirror Therapy – (Approx Time: 15 min)

During this 2 week period the co-investigator will try to contact the subjects 3 times per week to assess adherence to the MT treatment and acquire pain diary and medication changes data. We are going to try maximum 2 attempts per day.

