**Visit 14:**

Last day of mirror therapy - (Approx Time: 3 hours)

*This visit will be scheduled in the last MT home session and the following assessments will be performed. This visit can be divided in two days if time allows and the subject agrees.*

Subject can perform the last mirror therapy session either at home or at the Neuromodulation Center.

After the MT session, subject will complete the following assessments:

- Visual Analogue Scale (VAS) for phantom limb pain
- Visual Analogue Scale (VAS) for Stump pain
- Visual Analog Scale (VAS) for Phantom Limb Sensation
- Visual Analog Scale (VAS) for Phantom Limb Telescoping
- Pain and Medication uses diary
- Stroop Test
- Health Survey SF-36
- Patients' Global Impression of Change (PGIC) scale
- Beck Anxiety Inventory
- Beck Depression Inventory
- Single and paired pulse TMS
- Side Effects Questionnaire for TMS
- fMRI evaluation

**Visit 15:** fMRI Evaluation – (Approximate Time: 1 hour)

*\*\*Visits 14 & 15 may be completed on the same day or broken up into two separate visit as the subject prefers*

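### The Aim 1 path analysis cannot separate mood relieving pain from pain relief lifting mood, so its direct/indirect split needs a reverse-direction model and a more limited claim

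*Combined protocol and SAP*

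**What the plan says.** The path analysis is described in the combined protocol and SAP, section VI, Statistical Analysis, under the heading for aim 1.

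- **Purpose.** It is to establish whether the pain reduction seen with the combined intervention "is due to direct effects versus indirect effects through improvement in secondary outcomes".
- **Decision rule.** A direct effect "can be assumed if the treatment effect cannot be explained by changes in psychological or functional outcomes".
- **Pain model.** Besides site, the covariates are baseline "pain, psychological changes, functional changes, and the covariate treatment (main effect of treatment").
- **Mediator models.** In addition, "separate regression models will be run to model the effects' of treatment on each outcome alone including all the secondary outcomes".
- **Timing.** The mixed model for pain uses "time (baseline and after treatment and follow-up) and the interaction group" by time. For the path analysis the section names no visit for mediator or outcome, no lag, no adjustment for interim pain, no pain-to-mood model and no sensitivity analysis for direction.

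The schedule is in section V. At Visits 4 to 12 the phantom limb pain VAS is taken before and after each session, and no mood or function scale is listed. Mood is first re-measured at Visit 13 ("Last day of tDCS session + Mirror Therapy"), with the pain VAS in the same post-session list. At Visit 14 one list ("After the MT session, subject will complete the following assessments") holds the pain VAS, SF-36, Beck Anxiety Inventory and "Beck Depression Inventory". Visit 16 has pain, anxiety and depression without SF-36. Visit 17 has all four.

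**The concern.** A model that adjusts pain for mood change and calls the lost part of the treatment effect indirect assumes that mood drives pain. The opposite is also plausible: treatment lowers pain, and lower pain improves depression, anxiety and quality of life. Mood change then carries information about pain change, and adjusting for it absorbs part of a treatment effect that never passed through mood.

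The schedule gives the analysis no protection. Pain is recorded from the first treatment session, while mood is not re-measured until after the tenth tDCS session and SF-36 not until Visit 14. No mediator is observed before pain could have moved.

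At stake is the mechanistic statement in the trial report. A treatment whose effect on pain is wholly direct could be described as working partly through mood or function.

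**Working it through.** **Inputs.** From section VI, Sample size calculation: means 5.2 and 6.4, SDs 1.5 and 1.6, two-sided alpha 0.05, power 80%, 27 per group, 132 in total. The documents give no pain-mood correlation, so r is an assumption and is shown over a range.

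**1. The plan's own figure.** It gives none for the path analysis, but its sample size fixes the scale.
- Pooled variance = (1.5² + 1.6²)/2 = 2.405, so SD = 1.551. The difference is 6.4 − 5.2 = 1.2.
- n = 2 × (1.960 + 0.842)² × 2.405 / 1.2² = 26.2, rounded up to 27 per group; 4 × 27 = 108. This reproduces the stated figure.

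**2. A wholly direct effect put through the planned model.** Let T be treatment, Y pain change and M mood change, with Y = τT + e and M = bY + u. The true indirect effect is zero.
- Treatment shifts M by bτ.
- Within arms, the slope of Y on M is b·var(e)/var(M).
- The product is τ × b²·var(e)/var(M) = τr², where r is the within-arm correlation of Y and M.
- The planned model therefore reports τ(1 − r²) as direct and τr² as indirect.

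With a true direct effect of 1.2 points (analytic columns, then simulation of 4,000 trials at 27 per group):

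| r | Share wrongly indirect | Direct effect, 1.2(1 − r²) | Direct effect significant | Both paths p < 0.05 |
|---|---|---|---|---|
| 0 | 0% | 1.20 | 79% | 0.1% |
| 0.2 | 4% | 1.15 | 78% | 2% |
| 0.3 | 9% | 1.09 | 74% | 7% |
| 0.5 | 25% | 0.90 | 64% | 28% |
| 0.7 | 49% | 0.61 | 46% | 49% |

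The last column uses a joint-significance test that the plan does not specify; the shrinkage does not depend on it. A larger sample does not help: at 33 per group (132/4) that column becomes 11%, 33% and 58% for r = 0.3, 0.5 and 0.7.

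**3. Several mediators.** The plan enters more than one, and r² is then replaced by their joint R². For three mediators each at r = 0.5 with residual correlation c, the pairwise correlation is 0.25 + 0.75c and R² = 0.75/(1 + 2 × (0.25 + 0.75c)). This is 0.75/1.5 = 50% at c = 0 and 0.75/2.25 = 33% at c = 0.5.

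**4. Would lagging alone cure it?** Take Visit 13 mood and Visit 14 pain, with residual pain correlation ρ between the visits. The false indirect share becomes ρr². It runs from 0.5 × 0.09 = 4.5% to 0.9 × 0.36 = 32% for ρ = 0.5 to 0.9 and r = 0.3 to 0.6. Adding Visit 13 pain takes the mood coefficient to about zero, which is correct in this scenario.

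**5. What that adjustment costs when mediation is real.** Suppose the whole 1.2 runs through Visit 13 mood and ρ = 0.6. Adjusting for Visit 13 pain leaves (1 − 0.6) × 1.2 = 0.48. In simulation at 27 per group the indirect effect is then detected in about 18%, 41% and 66% of trials at r = 0.3, 0.5 and 0.7, against about 60%, 98% and 97% without the adjustment.

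**The case against.** Four points deserve weight.

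*The plan does not say that it uses same-visit changes.* This stands. A reader might infer from the schedule that mediator and outcome come from one visit, but no visit is named, and Visit 13 mood with Visit 14 pain would also fit the wording. The defect is the absent ordering. Choosing a lag without further steps reduces the bias but does not remove it (step 4).

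*A reader might infer that the rule gives the wrong answer in the most likely case.* The documents do not support that. They give no correlation, so no value of r can be called likely, and at r = 0.2 the distortion is only 4%. Most of the direct effect survives at r = 0.3 and 0.5. If explained is read as a significant effect losing significance once mood is added, that happens in about 9%, 20% and 44% of trials with a significant total effect at r = 0.3, 0.5 and 0.7: a minority throughout.

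*The analysis is peripheral.* This stands in part. Aim 1 in the Specific Aims is about efficacy, the path analysis comes last, and secondary-outcome analyses are labelled exploratory. The bias also makes a direct-effect claim harder to reach, not easier. However, the path analysis is applied to the primary outcome with an explicit inferential rule, and an exploratory label does not correct a directional bias.

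*An obvious remedy can mislead in the other direction.* This also stands. A reader might conclude that an indirect effect should be claimed only from a lagged model adjusted for Visit 13 pain. Visit 13 follows all ten tDCS sessions, so that rule removes mediation already expressed in pain and would replace false indirect findings with false direct ones (step 5).

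**Conclusion.** The concern holds as a limit on what the path analysis can conclude. As specified, with no ordering and no reverse model, it can present a wholly direct effect as partly indirect, and the visit schedule offers no mediator measured before pain could have changed. For one mediator the false indirect share is r²: 9%, 25% and 49% at assumed r of 0.3, 0.5 and 0.7.

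The size rests on three assumptions: that pain relief improves mood or function, that there is no true mediation in the scenario, and the value of r. That the mediators are the Beck scales and SF-36 is a reading of the plan's general terms, and the timing is taken from the visit-by-visit lists. The primary group-by-time analysis and the sample size are not affected. The change should be made, but it does not threaten the trial's main result.

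**What to change.** 1. State in the SAP which visits supply mediator and outcome.
2. Fit the reverse model (treatment to pain change to depression, anxiety and SF-36 change) beside the planned one. In the wholly direct scenario of step 2, treatment has no remaining effect on mood once pain is in the model, so the comparison is informative.
3. Claim a direct or indirect split only if the two directions can be told apart. Otherwise report same-visit paths, including all SF-36 paths, as associations.
4. As a sensitivity analysis, fit a lagged model with baseline-to-Visit 13 change in depression and anxiety as mediators of pain at Visits 14 and 16. Show it both with and without adjustment for Visit 13 pain. State that the adjusted version understates a true indirect effect and that the unadjusted version keeps part of the reverse-direction bias.

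All the data are already scheduled. The cost is SAP wording, a few extra models and a weaker mechanistic conclusion. SF-36 cannot be tested in the lagged model because it is not taken at Visit 13.
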